3.4 Statistical Method

3.4.1 Statistical Design

This is a prospective randomized case study comparing outcomes between 2 groups of patients.

Descriptive statistics will be performed on patient characteristics such as age, and sexual make up amongst the participants.

Outcomes will be evaluated between the 2 groups using crosstab analysis of the data

Logistic regression analysis may be performed on the incremental wet dry data vs time to achieving dryness

3.4.2 Sample Size Considerations

A power calculation was performed using

<http://powerandsamplesize.com/Calculators/Compare-2-Proportions/2-Sample-1-Sided>

A 2 proportion 1 sided power analysis was performed A proportion of 0.5 was used for the SNEA and an expected outcome of 0.8 for the GoGoband® the sampling ratio is 1, the power was set to 0.8 and type 1 error rate of 5%. This gives a sample size of 29 participants.

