Randomized Study Of Novel Enuresis Alarm (GoGoband®)Vs Standard Bedwetting Alarm

Protocol Number
2000031281

NCT05214131

Protocol Version
February 20, 2024
Version #6

IDE Number:

IDE Holder:

PRINCIPAL INVESTIGATOR:

[name]., Ph.D.
Department of Urology
[contact]
Email Address: [contact]

Confidentiality Statement:

2000031281

February 20, 2024

REVISION HISTORY:

Include the IRB approved protocol version number and date for each revision of the protocol. All version history should remain in the table and never be deleted. The oldest IRB approved version of the protocol should be listed on the top row. The most recent IRB approved version should be listed on the bottom row.

Revision #	Version Date
1	Sept 1 2021
2	Sept 9 2021
3	November 18, 2021
4	December 28, 2021
5	Jan 15 2022
6	February 20, 2024

2000031281

February 20, 2024

Synopsis

Primary Objective
 
Identify the dry night rate in patients using the GoGoband® nocturnal enuresis device vs a standard Pflaunger bedwetting alarm.

Secondary Objective (if applicable)
 
to ascertain if familial incidence of nocturnal enuresis has an effect on outcomes

Study Duration: total 3 years, 2 years active with 1 year for analysis

Study Design
 
Include a high-level description of the study design.
 
This is a prospective randomized comparison of GoGoband® vs standard nocturnal enuresis alarm

Number of Study Sites
 
Study sites will include all clinic sites where patients are seen in the Yale New Haven Health System
 
Yale New Haven Children’s Hospital clinic WP2 Yale New Haven Children’s Hospital Longwharf Clinic Yale New Haven Children’s Hospital Trumbull clinic Yale New Haven Children’s Hospital Norwalk clinic Yale New Haven Children’s Hospital Greenwich Clinic

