
Study Population
 
Define the study population, source of the participants, and selection rationale. Study subjects should be representative of the population of interest. Provide a brief description of the study population (e.g., healthy/sick, children/adult, inpatient/outpatient, demographic groups), the characteristics of different study groups, if applicable, and the source of participants. Do not list inclusion/exclusion criteria here, as these will be listed in the upcoming sections.
 
Study population will consist of children seen in our Bladder and continence program who present with nocturnal enuresis. Patients will be evaluated with validated questionnaire to confirm that they are monosymptomatic nocturnal enuretics and will be asked if they wish to participate in the study if they are between 6 yrs and 21 years of age.

Number of Participants: 150 children and adolescents

Primary Outcome Variables

2000031281

February 20, 2024

Variables:

Wetting event: Dry or Wet

Did patient wear the device: yes or no used to measure compliance

Is the patient considered cured (dry 29/30 nights) : yes or no

Is the patient partially better (improvement of 50% or more compared to pre treatment)

Did the patient show no improvement (<50% improvement compared to Pre treatment)

Secondary and Exploratory Outcome Variables (if applicable)

Did parents wake to assist child when alarm goes off: yes or no (2 nd measure of compliance)

What is the role of parental assistance in Dry night rates

Is there a correlation with parental NE and response to alarm

2000031281

February 20, 2024

Abbreviations

Abbreviation	Explanation
MNE	Mono symptomatic nocturnal enuresis
NMNE	Non Mono symptomatic nocturnal enuresis
SNEA	Standard Nocturnal enuresis Alarm
DV	Dysfunctional Voiding
DVQ	Dysfunctional Voiding questionnaire
PPG	Photoplethysmography

Glossary of Terms

Glossary	Explanation
----------	-------------

Table of Contents

Preface.....	2
Synopsis	4
Primary Objective.....	4
Secondary Objective (if applicable).....	4
Study Duration.....	4
Study Design	4
Number of Study Sites.....	4
Study Population	5
Number of Participants.....	5
Primary Outcome Variables	5
Secondary and Exploratory Outcome Variables (if applicable).....	5
Abbreviations	6
Glossary of Terms	7
1 Introduction.....	11
1.1 Introductory Statement	11
2 Background.....	12
2.1.1 Device Preclinical Experience	12
2.1.2 Device Clinical Experience.....	12

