5.2 Outcome Variables

5.2.1 Primary Outcome Variables

Variables:

Wetting event: Dry or Wet

Did patient wear the device: yes or no used to measure compliance

Did patient take the medication: yes or no used to measure compliance

Is the patient considered cured (dry 29/30 nights) : yes or no

Is the patient partially better (improvement of 50% or more compared to pre treatment)

Does the patient show no improvement (<50% improvement compared to Pre treatment)

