5.3.1 Number of Participants

Number of participants: 100 total, 50 in each group GoGoband®, SNEA,

Number to be screened: 200

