6.1.2 Device Administration and Schedule

SNEA: Device Will be provided to the patient

1. Instruction will be provided on how to set up the device and use it
2. The device will be worn consecutively for 3 months.
3. The alarm use will be terminated if they have been dry for 3 months consecutively.

GoGoband®: Device Will be provided to the patient

1. Instruction will be provided on how to set up the device and use it
2. The device will be worn consecutively for 3 months
3. The device will follow the built in algorithm in the device to decide when to begin the weaning process.
4. The weaning process will occur automatically until there no more nights in which the system will sound impending urination alarms

Non-compliant patients will be removed from the study. Alarms will not be requested back from the participants.

Reasons for noncompliance will be the following

1. Not taking medication
2. Not using device
3. Not filling in and submitting biweekly logs.

If a bedwetting alarm breaks or is nonfunctional the device will be replaced, and the study will proceed from the last active day

Method of Assignment/Randomization (if applicable)

2000031281

February 20, 2024

Randomization will be accomplished by having 100 envelopes with 50 SNEA and 50 GoGoband® choices. The envelopes will be distributed to the sites and pulled randomly at each site.

Age matching:

After 50% enrollment in any group the average age and standard deviation of the group will be calculated and an effort to adjust enrollment so groups are age matched will be made.

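### Section 3.4.2 reports 29 participants where its inputs give 29 per group (58 total), enrolment is 150 in one place and 100 in another, and the outcome behind the calculation is not named

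*Combined protocol and SAP*

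**What the plan says.** Section 3.4.2 Sample Size Considerations (6.4.2 in the table of contents) states: "A 2 proportion 1 sided power analysis was performed". It assumes 0.5 for SNEA and 0.8 for GoGoband, a sampling ratio of 1, power 0.8 and a type 1 error rate of 5%. It concludes: "This gives a sample size of 29 participants". It does not say whether 29 is per group or in total, and it does not say which outcome the two proportions describe.

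The enrolment target appears in three places:

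- Synopsis: "Number of Participants: 150 children and adolescents".
- Section 5.3.1: "Number of participants: 100 total, 50 in each group".
- Method of Assignment/Randomization, within 6.1.2: "100 envelopes with 50 SNEA and 50 GoGoband® choices".

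The Synopsis gives the primary objective as follows: "Identify the dry night rate in patients using the GoGoband® nocturnal enuresis device", compared with a standard alarm. Section 3.4.3.1 lists six primary items: the nightly wet or dry result, device wear, medication use, cure (29 of 30 nights dry), improvement of at least 50%, and improvement below 50%. For the analysis, 3.4.1 says: "Outcomes will be evaluated between the 2 groups using crosstab analysis of the data". No test, sidedness or significance level is given there or in 3.4.3.1. Section 3.4.5 counts dropouts as failures in the success, partial or failure classification.

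**The concern.** A sample size statement should let a reader trace the enrolment target to one outcome and one test. Here the chain breaks in three places.

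1. The number 29 has no unit. A literal reader takes it as the whole trial, and the stated 80% power does not hold for that number.
2. The current text has two enrolment targets, so the point at which recruitment ends is not defined. The 100 envelopes cannot randomise 150 children. Neither 100 nor 150 is derived from 29 or 58.
3. With six primary items and no outcome attached to 0.5 and 0.8, the calculation supports no particular comparison. The comparison it was meant for could be chosen after the results are known. The one-sided calculation also cannot be matched to a crosstab with no stated sidedness.

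**Working it through.** **Inputs, all from 3.4.2:** p₁ = 0.5 (SNEA), p₂ = 0.8 (GoGoband), one-sided α = 0.05 (z = 1.645), power 0.80 (z = 0.842), ratio 1:1.

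**Step 1: reproduce the 29.** The usual formula with unpooled variance is

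n per group = [p₁(1−p₁) + p₂(1−p₂)] × [(z_α + z_β)/(p₂−p₁)]²

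= (0.25 + 0.16) × [(1.645 + 0.842)/0.3]² = 28.16 (with unrounded z values), rounded up to **29 per group, 58 in total**.

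The plan's figure is therefore reproduced, as a per-group number. The pooled-variance version gives 31 per group.

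**Step 2: power if 29 were the total.** This uses full enumeration of the binomial outcomes and the Pearson z test without continuity correction, one-sided.

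| SNEA / GoGoband | Power |
|---|---|
| 14 / 14 | 0.525 |
| 15 / 14 | 0.555 |
| 15 / 15 | 0.556 |
| 14 / 15 | 0.589 |
| 29 / 29 | 0.796 |

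A total of 29 gives about 53–59%. The stated 80% belongs to 29 per group.

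**Step 3: power at the two enrolment targets.** Same method, 0.5 vs 0.8.

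| Per group (total) | One-sided 5% | Two-sided 5% |
|---|---|---|
| 50 (100) | 0.947 | 0.895 |
| 75 (150) | 0.990 | 0.977 |

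**Step 4: effect of sidedness.** With z = 1.960 in place of 1.645, the unpooled formula gives 35.76, or 36 per group; the pooled formula gives 39. In the exact calculation, 36 per group has 78.7% two-sided power, so the unpooled figure is slightly optimistic. At 29 per group, power falls from 80% one-sided to 67% two-sided. Fifty per group covers every one of these requirements.

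**Step 5: dropouts as failures.** This step applies only if the outcome is at patient level and 0.5 and 0.8 are rates among completers. Each rate is then multiplied by (1−d). The dropout rates d are assumptions and are taken as equal in both groups. The only related figure in the plan is about 30% abandonment for existing alarms (section 2.2). Power at 50 per group:

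| d (assumed) | Rates compared | One-sided | Two-sided |
|---|---|---|---|
| 10% | 0.45 vs 0.72 | 0.869 | 0.802 |
| 30% | 0.35 vs 0.56 | 0.668 | 0.584 |

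If 0.5 and 0.8 already count dropouts as failures, this loss does not arise.

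**The case against.** The strongest reply is that nothing operational depends on the missing label. Section 3.4.2 gives every input and names its calculator, so a statistician can recover 29 per group in a minute. Section 5.3.1 and the envelopes both plan 50 per group, and nobody proposes to enrol 29 children in total. On that view the 53–59% describes a trial that does not exist. This stands: the figure shows only what the sentence says if read literally, and it is not a forecast for this trial.

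A reader might go further and infer that the trial is underpowered. The documents do not support that. On the stated inputs both enrolment targets exceed 80% power, one-sided and two-sided.

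A reader might also infer that the dropout rule will erode the power. That cannot be concluded either. The plan gives no dropout rate for GoGoband and no expected difference between groups, and it does not say whether 0.5 and 0.8 already include dropouts. The figures in step 5 are conditional illustrations.

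It can also be said that 100 is clearly the working figure, since the two operational sections agree on it. That is likely, but the Synopsis is current text and not an amendment log, and only the sponsor can say which figure is intended.

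Finally, the 0.5 may come from section 2.2, which says that few publications exceed 50% success under a four-week dryness standard. Section 3.4.2 does not make that link, so the outcome remains unnamed. None of these replies resolves the enrolment conflict or the missing outcome.

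**Conclusion.** The point holds as a correction to the sample size statement and the enrolment target. The 29 is arithmetically right per group and wrong as written, because the required total is 58. The targets of 150 and 100 contradict each other and neither is tied to the calculation. The outcome behind 0.5 and 0.8 and the sidedness of the crosstab need to be stated so that the calculation matches the primary analysis.

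Power on the stated inputs is about 95% one-sided and 89% two-sided at 50 per group, and 99% and 98% at 75 per group. These figures assume a patient-level binary outcome, a Pearson test without continuity correction, and that 0.5 and 0.8 are the rates as analysed. The missing sidedness and dropout allowance are mainly gaps in detail at 50 per group. The change should be made, but the trial's size is not in question on its own inputs.

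**What to change.** 1. In 3.4.2, write 29 per group (58 total).
2. Reconcile the Synopsis figure of 150 with the 100 in 5.3.1 and the envelopes. State one enrolment target throughout and give its power on the stated inputs.
3. Before outcomes are compared between groups, name the single primary outcome that 0.5 and 0.8 refer to. Use the same sidedness in the calculation and in the crosstab. A two-sided 5% test needs about 36–39 per group depending on the formula, which 50 covers. The plan does not state enrolment status, so the amendment should record that the choice was made before any such comparison.
4. As a minor addition, say whether 0.5 and 0.8 already count dropouts as failures under 3.4.5. If they do not, restate power under that rule over an assumed range. For example, at 50 per group power is 87% one-sided and 80% two-sided for 10% dropout in both groups, and 67% and 58% for 30%.

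The cost is a set of short text edits. They need an approved IRB amendment, as the Institutional Review Board section requires. No added patients or new data are needed to reach 80% power on the stated inputs. The stated power may become less favourable if the two proportions turn out to be completer rates or if a two-sided test is chosen.

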3.4.3 Planned Analysis

3.4.3.1 Primary Analyses

Outcomes will be evaluated between the 2 groups using crosstab analysis of the data for the following data :

Wetting event: Dry or Wet

Did patient wear the device: yes or no used to measure compliance

Did patient take the medication: yes or no used to measure compliance
 Is the patient considered cured (dry 29/30 nights) : yes or no
 Is the patient partially better (improvement of 50% or more compared to pretreatment)
 Does the patient show no improvement (<50% improvement compared to Pretreatment)
 Logistic regression analysis may be performed on the incremental wet dry data vs time to achieving dryness

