BACKGROUND: Bedwetting alarms (BWA) have been around for more than half a century with little innovation in the field. GOGOBand® utilizes real time heart rate variability (HRV) analysis and applied artificial intelligence (AI) to create an alarm that is capable of waking the patient prior to wetting. Our Aim was to evaluate the efficacy continues to remain high with the addition of 20 new patients to our servers. **METHODS:** Data was retrieved and analyzed from our servers, of patients who purchased the GOGOBand® which includes a heart rate monitor, moisture sensor, bedside tablet and app for the parents phone in this study. There are 3 modes, training, where the individualized HRV parameters are used to build the alerting model. Once patients are done with training, they enter the Predictive mode where they receive an alarm if an impending urination event is noted. In Weaning mode the alerting is gradually suppressed. Only patients that used the alarm for more than 30 days were included. Data analysis was done with SPSS and xlstat. **RESULTS:** A total of 60 subjects that have used the system for more than 30 nights were included in this analysis. Gender mix was 46 males (76.6%) and 14 females (23.3%). The mean age of the subjects is 10.2 yrs. Subjects wet the bed an average of 6.2 nights per week prior to treatment. Severity and number of accidents per night had no impact on the ability to achieve dryness with the GOGO Band® device in logistical regression analysis. The data was also segregated based on compliance since it became clear during the analysis that compliant patients achieved better results than non-compliant patients. A crosstab analysis was performed and is reported in table 1. The data clearly indicates that compliant patients >80% are able to remain dry 96% of the time once they enter the weaning phase. **CONCLUSIONS:** Our findings indicate a 96% success rate in patients that are weaning, this translates to 1.2 wet nights per 30 days. This compares to the same group when starting the use of the alarm had only 14.4 dry nights per 30 days. The addition of the 20 patients indicates that that our results are enduring and seem to be improving as we continue to increase the number of patients that are on the system.

compliance groups		training	predictive	Wean	Total	
<=65%	dry	Count	311 _a	881 _b	1584 _c	2776
		% within group	59.70%	77.30%	87.50%	80.00%
	wet	Count	210 _a	258 _b	226 _c	694
	% within group	40.30%	22.70%	12.50%	20.00%	

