5.1 General Design Description

We propose the following study in patients who have been evaluated for primary nocturnal enuresis in our Yale New Haven Clinics.

- All patients to be evaluated for nocturnal enuresis will undergo standard evaluation and initial treatment for nocturnal enuresis which includes:
 - Assessment Of Bowel Habits,
 - Fill Out A Questionnaire To Evaluate For Voiding Dysfunction
 - Treatment with routine bedwetting protocol of:
 1. Stopping drinks 1 HR before bedtime, meals at least 3 hrs before bedtime, eliminating milk and ice cream from dinner and on, making sure that bowel movements are occurring 4 times per week and treating appropriately if necessary.
 2. On return visit bedwetters and parents will be given the option of using medication , no further treatment, or alarm therapy.
 3. If patients choose alarm therapy, they will be asked if they wish to participate in the Randomized study comparing GoGoband® vs SNEA.
 4. Alarms will be provided to the patients free of cost to participants
 5. Patients in the alarm group will be treated for 3 months continuously.
 6. Patients in the SNEA group will record nightly if they wet their clothes and the report will be recorded and reviewed weekly
 7. GoGoband® patients' data will be automatically saved on the HIPPA Compliant servers and subsequently reviewed at the end of the week.

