5.1.1 Study Date Range and Duration

Each patient will be in the study for 90 days. The study duration will be 2 years to accrue enough patients willing to participate in the study and 1 year for data analysis and publication

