3.4.3.7 Other

3.4.4 Subsets and Covariates

3.4.5 Handling of Missing Data

Patients who drop out of the study will be considered failures for purposes of the study with regards to success vs partial or failure analysis
 Dry /wet night rates will be maintained for the overall analysis of overall dry/wet ratios regardless of the patient ceases participation

4 Trial Administration

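### The primary dry/wet crosstab pools nights and treats up to 90 nights from one child as independent, so its p-value will badly overstate the evidence

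*Combined protocol and SAP*

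**What the plan says.** The Synopsis gives the primary objective as "Identify the dry night rate in patients using the GoGoband" device against a standard alarm. Section 3.4.3.1 (Primary Analyses) says "Outcomes will be evaluated between the 2 groups using crosstab analysis of the data for the following data", and the list that follows opens with "Wetting event: Dry or Wet".

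That variable takes a value each night. Section 5.1 says "Patients in the SNEA group will record nightly if they wet their clothes", section 3.2.1 has a nightly log in both arms, and section 5.1.1 says "Each patient will be in the study for 90 days".

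Section 3.4.5 handles two kinds of outcome differently. Success, partial response and failure are scored per patient, with dropouts counted as failures. For the nightly data it says "Dry /wet night rates will be maintained for the overall analysis of overall dry/wet ratios regardless of the patient ceases participation".

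The only other model named for the nightly data is optional: "Logistic regression analysis may be performed on the incremental wet dry data vs time to achieving dryness". Section 3.4.3.2 adds a logistic regression of parental assistance on dry-night rates. No section mentions a dry-night rate per child, clustering, GEE, a mixed model or robust standard errors.

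**The concern.** The child is randomised, not the night. Some children become dry at once and others keep needing the alarm (section 2.1.1), so nights from one child resemble each other. A crosstab has no term for this. It counts each night as a fresh, independent observation, so its standard error is too small.

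The dry-night rate is the synopsis primary objective, and the plan does not rank its primary variables. A spuriously significant night-level result could therefore be presented as the main finding.

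Pooling has a second effect: it weights children by how long they stay. A child who leaves early because the alarm is not working contributes few nights, mostly wet, so the pooled rate in that arm looks better than the average child's experience.

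**Working it through.** **The plan's own figure.** Section 3.4.2 uses 0.5 against 0.8, one-sided 5%, power 80%, ratio 1. With the unpooled formula, n = [0.5×0.5 + 0.8×0.2] × ((1.645 + 0.842)/0.3)² = 28.16, rounded up to 29. The stated 29 is reproduced as a per-group number. The sample size arithmetic is not at fault, and its unit is the participant.

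**Evidence that nights are pooled.** The 60-patient abstract in section 2.1.2 says "A crosstab analysis was performed and is reported in table 1". The cells of that table sum to 2776 + 694 + 560 + 169 + 661 + 82 = 4,942. These are nights from 60 children, about 82 each, and they carry significance letters at the 0.05 level. Section 3.4.5 keeps the nights of children who stop, for an overall ratio. No section points the other way.

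**Inputs.** 50 children per arm (section 5.3.1) and 90 nights each (section 5.1.1) give 50 × 90 = 4,500 nights per arm. The intraclass correlation (ICC) is not in the documents, so a range is assumed.

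**Formulas.** Design effect D = 1 + (90 − 1) × ICC. Effective nights per arm = 4,500 / D. True error of a nominal 5% test = 2 × [1 − Φ(1.96/√D)] two-sided, or 1 − Φ(1.645/√D) one-sided.

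| Assumed ICC | D | Effective nights per arm | True error, one-sided | True error, two-sided |
|---|---|---|---|---|
| 0.01 | 1.89 | 2,381 | 12% | 15% |
| 0.05 | 5.45 | 826 | 24% | 40% |
| 0.10 | 9.9 | 455 | 30% | 53% |
| 0.20 | 18.8 | 239 | 35% | 65% |
| 0.30 | 27.7 | 162 | 38% | 71% |
| 0.50 | 45.5 | 99 | 40% | 77% |

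A beta-binomial simulation (20,000 trials per ICC, assumed dry rate 70% in both arms) gave two-sided errors of 15.8%, 40.8%, 53.1%, 65.6%, 71.1% and 77.3%. A t-test on one proportion per child gave 4.8% to 5.4% throughout. With only 60 or 30 nights per child at ICC 0.10, the two-sided error is still 46% or 32%. The error formulas do not involve the number of children, so the conflict between 150 participants (Synopsis) and 100 (section 5.3.1) does not affect these rates.

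**Is the ICC range plausible?** As an illustration, assume half the children are dry 29 of 30 nights (the section 3.4.2 control proportion read as a cure rate) and the rest are dry on a fraction q of nights. The ICC is then [(0.967 − q)/2]² / [m(1 − m)], with m the mean of the two rates. For q = 0.80, 0.65 and 0.50 this gives 0.07, 0.16 and 0.28, with simulated two-sided errors of 46%, 63% and 70%. For q = 0.90 the error is 23%.

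**Effect on a result.** Assume 80% against 75% dry nights on 4,500 nights per arm. The naive z is 0.05 / √(0.775 × 0.225 × 2/4,500) = 5.68, p = 1.3 × 10⁻⁸. Dividing z by √D gives p = 0.015, 0.07, 0.19 and 0.28 at ICC 0.05, 0.10, 0.20 and 0.30.

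**Weighting.** Assume 30% leave at night 30 with 40% dry nights, and the rest are 85% dry over 90 nights.

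- Pooled: (0.3×30×0.40 + 0.7×90×0.85) / (0.3×30 + 0.7×90) = 57.15/72 = 79.4%.
- Mean per child: 0.3×0.40 + 0.7×0.85 = 71.5%.

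**The case against.** The strongest reply is that the plan never says in words that nights are pooled or treated as independent. Section 3.4.3.1 names no unit and no test, and the pilot abstract is background rather than this trial's plan. This stands as far as it goes: pooling is an inference. But a crosstab has no place for repeated nights, the missing-data text and the pilot point the same way, and nothing points to a per-child analysis. If one was intended, the same change of wording would say so.

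Several narrower points also stand:

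- The cured, partially better and no-improvement outcomes are one value per child and are unaffected. The fault lies in the dry/wet item, and in device wear if that is crossed by night.
- The primary objective in section 4.2 does not name the dry-night rate; the Synopsis does.
- The only sidedness in the plan is the one-sided 5% of section 3.4.2, so the lower error column matches it best. It is still far above 5%.
- The logistic regression is optional and its outcome is unclear. It shares the fault only if nights are entered without a clustering term.
- Weighting by length of stay is separate from independence. The example describes one arm; a bias between arms needs different patterns of leaving.

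The missing ICC does not rescue the plan, because the error more than doubles even at 0.01.

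**Conclusion.** The concern holds. On the only reading the text supports, the night-level crosstab is an anticonservative test of the synopsis primary objective. For ICCs of 0.05 to 0.30, a nominal 5% test of two equally effective alarms rejects about 24% to 38% of the time one-sided and 40% to 71% two-sided. These figures assume 90 nights from every child and an ICC range the documents do not supply. Shorter follow-up or a lower ICC reduces the inflation but, across the ranges checked, does not remove it. This must be fixed before analysis.

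**What to change.** In section 3.4.3.1, replace the night-level crosstab with one of the following:

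- Each child's dry-night proportion over a fixed window, compared between arms in a linear model with one value per child, adjusted for age and pre-treatment wet nights per week.
- A logistic GEE or mixed model on nights, with child as the cluster and robust standard errors.

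State which is the main analysis. State also how nights after a child leaves are counted, since neither method settles that. Counting them as wet would match the plan's rule that dropouts are failures; an analysis of observed nights only could then serve as a sensitivity check.

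Keep crosstabs for the child-level outcomes. Apply the same clustering to the parental-assistance regression in section 3.4.3.2 and to any regression on nightly data.

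The cost is protocol wording and slightly more analysis work. No new data item is needed: pre-treatment wetting frequency is already required for eligibility (section 5.3) and for the improvement outcomes. No baseline diary is described, however, so the plan should say how that frequency is obtained. The downside is a wider, honest confidence interval.

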4.2 Primary Objective

The primary objective of this study is to determine whether the GoGoband®] is as effective or more effective in comparison to children who use SNEA in a population of MNE patients with no underlying ADHD in a 3 month period.

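### Several outcomes are labelled primary and none is named as deciding, so the chance of a false positive across the efficacy tests is roughly 8–16% rather than 5%

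*Combined protocol and SAP*

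**What the plan says.** - **Outcome list.** Under "5.2.1 Primary Outcome Variables" the protocol lists six items: nightly wet/dry, device worn, medication taken, cured (29 of 30 nights dry), improved by at least 50%, and improved by less than 50%. The Synopsis gives the same list without medication, so five.
- **Analysis.** Section 3.4.3.1 repeats the six: "Outcomes will be evaluated between the 2 groups using crosstab analysis of the data for the following data". It adds an optional logistic regression. It ranks nothing and splits no alpha.
- **Objective.** The Synopsis objective is to "Identify the dry night rate in patients using the GoGoband® nocturnal enuresis device" against a standard alarm, and section 3.1 also speaks of comparing dry night rates. Section 4.2 asks whether the device "is as effective or more effective in comparison to children who use SNEA" and names no outcome.
- **Sample size.** Section 3.4.2 reports a one-sided calculation for two proportions with equal arms and 80% power. It takes a rate of 0.5 under the standard alarm against 0.8 under the new device, at a "type 1 error rate of 5" per cent. It does not say which outcome the two rates describe.
- **Drop-outs.** Section 3.4.5 counts them as failures in the success/partial/failure analysis, but keeps whatever nights they recorded in the overall dry/wet ratio.

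**The concern.** A 5% error rate protects one prespecified test. Here several efficacy outcomes share the primary label, each is compared between arms, and nothing says which result decides the trial. Two consequences follow.

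First, the chance that at least one comparison is significant when the alarms do not differ exceeds the 5% that the sample size section claims.

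Second, the deciding outcome can be settled after the data are seen. The candidates can disagree, because section 3.4.5 treats drop-outs differently for the response classes and for the dry/wet ratio. The outcome list also gives no window for the 30 nights within the 90-day study. No blinding is described, the device company supplies the alarms (section 4.17) and the principal investigator enters the logs (sections 4.5 and 4.8). A result resting on an endpoint not fixed in advance would therefore be hard to defend.

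**Working it through.** **1. The plan's own figure.** Inputs from section 3.4.2: rates 0.5 and 0.8, one-sided 5%, power 0.80, ratio 1. The unpooled formula gives

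n = [0.5×0.5 + 0.8×0.2] × ((1.645 + 0.842)/0.3)² = 0.41 × 68.7 = 28.16, rounded up to 29.

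This reproduces the stated 29, read as a per-arm number. It is the size for one comparison at one 5% level.

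**2. How many tests count.** Medication cannot be tabulated, because neither arm receives any. Device wear is marked in the text as a compliance measure. What remains is efficacy:
- two tests, if dry rate and one response measure are used;
- three, if partially better includes the cured, since no improvement is then its complement;
- four, if cured, partial and none are exclusive classes tabulated one by one beside the dry rate.

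**3. Independent tests at 5% each.**
- Two: 1 − 0.95² = 9.75%
- Three: 1 − 0.95³ = 14.3%
- Four: 1 − 0.95⁴ = 18.5%. This overstates the four-test reading, because exclusive classes of one classification are strongly dependent.

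**4. Allowing for correlation (assumed).** Three equally correlated normal tests, two-sided, give 12.5% at correlation 0.5, 10.9% at 0.7 and 8.4% at 0.9. One-sided, the values are 11.8%, 10.3% and 8.0%.

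**5. Simulating the trial's own outcomes.** Settings: no treatment difference; 50 per arm; 20,000–40,000 runs; each child's nightly dry probability drawn from one of five assumed beta distributions; baseline wet rate uniform from 2/7 (the eligibility minimum of two nights a week) to 1; dry rate summarised per child. The chance of at least one false positive, as the range over the five distributions, was:

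| Efficacy tests | Two-sided | One-sided |
|---|---|---|
| Cured, dry share | 8.4–9.7% | 8.5–8.9% |
| Cured, improved (including cured), dry share | 10.9–12.7% | 10.1–11.7% |
| Cured, partial, none (exclusive), dry share | 14.2–16.2% | 13.3–15.2% |

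Every reading is above 5%.

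**6. Size after the fix.** One test at one-sided 5% keeps the plan's 29 per arm (31 with the pooled-variance formula). At 50 per arm the pooled power is about 94%. A two-sided 5% test needs 0.41 × ((1.960 + 0.842)/0.3)² = 35.8, so 36 per arm, by the unpooled formula. The pooled formula gives (1.960×√(2×0.65×0.35) + 0.842×√0.41)²/0.3² = 38.5, so 39. Power at 50 per arm is then about 89%. These figures apply only to a per-child outcome with rates 0.5 and 0.8.

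**The case against.** The best reply is that the documents do indicate a lead outcome. The Synopsis objective and section 3.1 both name the dry night rate, and section 3.4.5 can be read as treating cured/partial/failure as one classification, hence one crosstab. That leaves two efficacy analyses, not six. This stands as a limit on the count, and it is why the lower end of the range is about 8%. It does not remove the point, because section 3.4.3.1 gives the dry night rate no priority and two tests at 5% still exceed 5%.

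A second reply concerns direction. If the crosstabs are two-sided, only half of the false positives favour the new device: 1 − 0.975³ = 7.3% for three independent tests. That is correct, but the matching nominal figure is 2.5%. The only sidedness the plan states is one-sided at 5%, and under it the 14.3% returns.

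Three stronger readings may tempt a reader, and the documents do not support them:
- **Six primary tests, hence 1 − 0.95⁶ = 26.5%.** One item cannot be tabulated, one is a compliance measure, and three are overlapping response classes.
- **A difference in device wear could be claimed as primary success.** The text marks this item as a measure of compliance, so it would not support an efficacy claim.
- **The power calculation shows that cure is the intended endpoint.** Section 3.4.2 names no outcome, and 50% improvement is also a per-child proportion. The 0.5 resembles the four-week-dry success rates discussed in section 2.2, but no section gives a cure rate of 0.8 for the new device; its background results are dry-night rates.

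**Conclusion.** The point holds in a limited form. Several efficacy outcomes carry the primary label, each is compared between arms, and no rule says which decides, while the plan budgets one 5% error for one unnamed outcome. The chance of at least one false positive is roughly 8–16%, about 1.6 to 3 times nominal.

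The range rests on assumed correlations and assumed between-child distributions. It also supposes that each test on its own holds 5%, which requires the nightly data to be summarised per child. Pooling nights as if independent would be a separate and larger problem, which this range does not cover.

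The matter should be settled before analysis, and the planned 50 per arm leaves room to do so.

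**What to change.** In section 3.4.3.1, with 5.2.1 and the Synopsis aligned:

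- Name one per-child primary outcome. State its time window, the sidedness of the test and the drop-out rule, including how children removed for non-compliance (section 3.3.7) are counted.
- State in section 3.4.2 which outcome the 0.5 and 0.8 rates describe. The choice is the sponsor's:
  - Per-child dry-night share matches the stated objective but needs its own sizing statement, with an assumed between-child standard deviation.
  - Cured (29 of 30), with drop-outs as failures, is a per-child proportion and can use the existing two-proportion calculation. Choosing it would move the dry night rate out of the lead, so the Synopsis objective would have to be reworded.
- If the test is made two-sided, restate the size as about 39 per arm. This is within the 50 per arm of section 5.3.1; the Synopsis total of 150 is larger still and should be reconciled with the 100 there.
- Label the remaining efficacy outcomes secondary, without confirmatory claims. Report device wear descriptively as compliance. Delete the medication item.

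This needs an amendment to the wording and no new data. The downside is that the other outcomes lose confirmatory status.
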